**With this revisions to our PT4A strategy, will this prototype do the following for you.**

**Intervention Appropriateness Measure (IAM)**

	Completely disagree	Disagree	Neither agree nor disagree	Agree	Completely agree
1. The HIT-Peer Delivery system seems fitting.	①	②	③	④	⑤
2. The HIT-Peer Delivery system seems suitable.	①	②	③	④	⑤
3. The HIT-Peer Delivery system seems applicable.	①	②	③	④	⑤
4. The HIT-Peer Delivery system seems like a good match.	①	②	③	④	⑤

<https://doi.org/10.1186/s13012-017-0635-3>

**Peers and Technology for Adherence, Access, Accountability, and Analytics (PT4A) Study**

**Study Instrument: Acceptability of Intervention Measure (AIM) for PEERS**

Study ID:	Date:			
Age:	Gender:			
1. Education/ Elimu	 No formal education/ Hakuna elimu rasmi			
 Primary/ Shule ya Msingi	 Secondary/ Shule ya Upili			
 Beyond secondary/ Zaidi ya Shule ya Upili maalum	 Special training e.g Trade. Insert Mafunzo kwa mfano biashara			
2. What is your main source of income?/ Chanzo chako kikuu cha mapato ni nini?				
 Farming/ Ukulima	 Business/Trade/Biashara	 Teacher/ Uwaalimu		
 Health worker/ Mfanyakazi wa afya	 Other/s (Insert): Ingine			
3. How long have you worked as a peer?				
4. What is your estimated monthly income in KES?/ Je! Mapato yako ya kila mwezi yanakadiriwa ngapi				
 KES? <1,000	 1,000-2,999	 3,000-4,999	 5,000-9,999	 >10,000
5. How long have you been living with hypertension/pressure in months? Umeishi kwa muda gani na shinikizo la damu / shinikizo (kwa miezi)				
 <6 months/ Miezi sita	 Between 6 months – 1year/ Kati ya miezi sita na mwaka			
 Between 1-2 years/ Kati ya mwaka mmoja na mbili?	 >2 years/ Zaidi ya miaka mbili?			
6. Where do you mainly seek treatment for hypertension/pressure?/ Unapata wapi matibabu ya shinikizo la damu				
 Health facility/ Kituo cha afya	 Pharmacy (over the counter medication) Duka la dawa (juu ya dawa ya kaunta)			
 Herbalist / Mtaalam wa mimea	 Other specify/ Nyingine taja			
 Not yet sought care/ Bado sijatafuta huduma				
7. About how long would it take to get from your home to the nearest chemist/pharmacy if you walked to them? Je! Itachukua muda gani kutoka nyumbani kwako kwenda kwa duka la dawa iliokaribu ukitembea?				
 Less than 15 minutes/ Chini ya dakika 15	 16-30 minutes/ Dakika 16-30			
 31 minutes to an hour/ dakika 31 hadi saa moja	 More than one hour/ Zaidi ya saa moja			
8. About how long would it take to get from your home to the nearest healthcare facility if you walked to them?/ Je! Itachukua muda gani kutoka nyumbani kwako kwenda kituo cha huduma ya afya kilicho karibu ikiwa utatembea kuelekea huko?				
 Less than 15 minutes/ Chini ya dakika 15	 16-30 minutes/ Dakika 16-30			
 31 minutes to an hour/ dakika 31 hadi saa moja	 More than one hour/ Zaidi ya saa moja			

**Instructions to Study Personnel:** *Read all questions aloud to the patient and record answers on questionnaire form.*

You were selected to take part in this survey because we value the knowledge you have on our topic of discussion. I kindly request for your honest opinions and ideas. There is no wrong or right response.

You should feel free to say whatever you think and feel.

*There is a plan to start a project that will support people living with hypertension/pressure at the community level. The purpose of the project is to assist these individuals take hypertension/pressure medication their as required through a peer-led project. A peer will be someone who is living with hypertension/pressure in the community and has been successful in managing their hypertension. The peer will be responsible for a number of things:*

- *Deliver hypertension medication to people living with hypertension/pressure at their most convenient location (door-to-door medication delivery).*
- *Provide psychological support to people living with hypertension/pressure during medication delivery and whenever needed.*
- *Record the health progress of people living with hypertension/pressure in a mobile device whenever they are in contact with a person living with hypertension/pressure.*
- *Using the mobile device, communicate with a clinician where the individuals living with hypertension receive care to discuss their health progress.*
- *Whenever necessary enable a conversation (either audio or video) between the clinician and the patient using the mobile device at the patient's convenient location.*
- *Insert the revised prototype*

	Completely disagree	Disagree	Neither agree nor disagree	Agree	Complete agree
1. The HIT-Peer Delivery system meets my needs	①	②	③	④	⑤
2. The HIT-Peer Delivery system is appealing to me.	①	②	③	④	⑤
3. I like the HIT-Peer Delivery system.	①	②	③	④	⑤
4. I would like to be enrolled in the HIT-Peer Delivery system.	①	②	③	④	⑤

**With this revisions to our PT4A strategy, will this prototype do the following for you?**

#### **Intervention Appropriateness Measure (IAM)**

	Completely disagree	Disagree	Neither agree nor disagree	Agree	Complete agree
The HIT-Peer Delivery system seems fitting.	①	②	③	④	⑤
The HIT-Peer Delivery system seems suitable.	①	②	③	④	⑤
The HIT-Peer Delivery system seems applicable.	①	②	③	④	⑤
The HIT-Peer Delivery system seems like a good match.	①	②	③	④	⑤
Total Score:					

## Subaim 2.2: Conduct a pilot of the intervention and evaluate feasibility

### AIM 2.2 Study Instrument: EVALUATION OF FEASIBILITY QUESTIONNAIRE FOR PATIENTS

*Hello, my name is \_\_\_\_\_. I am a research assistant for the PT4A study. I am approaching you as you have participated as a patient in the PT4A program and as such our feedback would be helpful for the program. I would like to ask you some questions to learn about your experiences with the PT4A program. I will ask you questions about your physical health, your mental health, and how you feel when you interact with a peer from the PT4A program. Your answers will help me understand what types of services people who are living with high blood pressure need to stay healthy.*

.

*Do you have any questions?*

*Ok, let's begin*

*Now I would like to hear about your experience with the PT4A peer delivery program. Please answer honestly and to the best of your knowledge. All responses are confidential.*

1. When you receive medication and counseling from a peer, how often do the peers treat you with courtesy and respect?

- All the time
- A lot of the time
- Some of the time
- None of the time

2. When you receive medication and counseling from a peer, how often do the peers listen carefully to you?

- All the time
- A lot of the time
- Some of the time
- None of the time

3. When you receive medication and counseling from a peer, how often do the peers ask for your opinion regarding your healthcare?

- All the time
- A lot of the time
- Some of the time
- None of the time

4. When you receive medication and counseling from a peer, how often are you satisfied with the amount of time your peer spends with you?

- All the time
- A lot of the time
- Some of the time
- None of the time

Please tell me how much you agree or disagree with the following statements

5. The peers in the PT4A delivery program can be trusted to keep my medical information private and confidential.

- Strongly agree
- Agree
- Disagree
- Strongly Disagree

6. Whenever you had questions about your medications or health which you brought up to the peer, how often were you satisfied about the answers you received from the peer?

- All the time
- A lot of the time
- Some of the time
- None of the time

7. When you receive medication and counseling from a peer, how often did you get clear instructions on how to use/take the medication?

- All the time
- A lot of the time
- Some of the time
- None of the time

8. Did you feel the peer having the Mobile Device helped with record keeping for the next clinical encounter you had with your doctor?

- Strongly agree
- Agree
- Disagree
- Strongly Disagree

Do you feel that the use of the mobile device helped you to manage the arising medical issue that came up?

- Strongly agree
- Agree
- Disagree
- Strongly Disagree

10. Did the use of a peer to deliver medication has improve your health?

- Strongly agree
- Agree
- Disagree
- Strongly Disagree

11. Did the use of a peer to offer psychosocial support help you improve your quality of life?

- Strongly agree
- Agree
- Disagree

Strongly Disagree
11. Has the use of a peer to deliver medication helped you to adhere to medication and you have experienced few if no symptoms associated with Hypertension
 Strongly agree
 Agree
 Disagree
Strongly Disagree

**AIM 2.2 Study Instrument: EVALUATION OF DELIVERY PROCESS AND COMPLETENESS QUESTIONNAIRE FOR PATIENTS**

*Now I would like to hear about your feedback on the PT4A medication delivery process. Please answer honestly and to the best of your knowledge. All responses are confidential.*

**Successful/proper deliveries**

The peers delivered the right medication as requested

- All the time
- A lot of the time
- Some of the time
- None of the time

The medication was delivered on the date expected

- All the time
- A lot of the time
- Some of the time
- None of the time

The medication was delivered at the time expected

- All the time
- A lot of the time
- Some of the time
- None of the time

**Medication packaging**

The medication was properly sealed during the delivery

- All the time
- A lot of the time
- Some of the time
- None of the time

The medication was properly labeled and the dosage indicated

- All the time
- A lot of the time
- Some of the time
- None of the time

The medication was properly labeled and the dosage indicated

- All the time
- A lot of the time
- Some of the time
- None of the time

The peer was able to give you instructions for medication use

- All the time

 A lot of the time  Some of the time  None of the time
The medication brand changes were clearly communicated  All the time  A lot of the time  Some of the time  None of the time
The medication payments reflected the amount of medication received  All the time  A lot of the time  Some of the time  None of the time
Total Scores _____

## APPENDIX C. INTERVIEW GUIDES FOR FEASIBILITY EVALUATION

### **Peers and Technology for Adherence, Access, Accountability, and Analytics (PT4A) Study**

#### **Study Instrument: Focus Group Discussion (FGD) Guide for Clinical Team**

**FGD moderator:** \_\_\_\_\_

**FGD note taker:** \_\_\_\_\_

**Date:** \_\_\_\_/\_\_\_\_/2022

**County:** \_\_\_\_\_

**Start Time:** \_\_\_\_\_

**End Time:** \_\_\_\_\_

#### **FGD:**

- Inform the participants about the study guided by the study information sheet.
- Provide participants with an opportunity to ask questions.
- Obtain written consent from each participant privately. (2 copies per participants)
- Provide each participant with a copy of their signed informed consent form.
- Complete the demographic survey for each participant privately.

### **Demographic Survey**

Indicate or insert your responses as necessary			
1. Study ID:			
2. State your age (Years)			
3. Sex	Male	Female	
4. What is your primary role at the facility?	MO	CO	Nurse Other staff (specify)
5. How long have you served as a health provider?			
6. Have you interacted with patients living with Hypertension?	Yes	No	

**NB: To be completed for each participant**

**Summary of observations during FGD**

**Moderator and note taker:** In the space below, please provide a summary of the FGD session you just had including both verbal and non-verbal cues.

## **Focus Group Discussion Guide**

### **Clinical Team**

\*\*\*\*\*

#### **Opening Remarks**

Hello. My name is \_\_\_\_\_ XXX \_\_\_\_\_ and I will help guide our discussion today. Thank you for welcoming us to your community. \_\_\_\_\_ XXX \_\_\_\_\_ is also present today to help take notes during our discussions. We will also be recording this session using a tape recorder (show the participants the tape recorder). This will help us capture what you say without missing out on anything. Your opinions and experiences are very important to us since it will help us understand how to develop health program to assist individuals living with hypertension in your community.

You were selected to take part in this discussion because we value your feedback regarding your experience in PT4A program I kindly request for your honest opinions and ideas. There is no wrong or right response. You should feel free to say whatever you think and feel. You are welcome to say as much or as little as you want. I am eager to hear what you have to say. Do you have any questions about what I have said so far?

#### **FGD rules**

Before we start, I would like as to you mention some of the rules that will guide our discussion

1. There are no right or wrong answers. We expect that you will have differing points of view. Please feel free to share your point of view even if it differs from what others have said.
2. We are recording this session as we discussed, because we do not want to miss any of your comments. No names will be included in any reports. Your comments are confidential. Please speak loudly for I want to be accurate in capturing what you say.
3. Don't feel like you have to respond all the time. But if you want to follow up on something that someone has said, you want to agree, or disagree, or give an example, feel free to do that.
4. I am here to ask questions, listen, and make sure everyone has a chance to share. We're interested in hearing from each of you. So if you are talking a lot, I may ask you to give others a chance. We just want to make sure all of you have a chance to share your ideas.
5. If you have a cell phone, please put it on quiet mode.

Now let us start discussions about your perceptions about the PT4A Intervention.

A. PT4A intervention:

PT4A project was started to support people living with hypertension/pressure at the community level. The purpose of the project was to assist these individuals take hypertension/pressure medication as required through a peer-led project. This peer led project used a mobile device similar to regular mobile phone, a smart phone, or a tablet. The mobile device enabled us to deliver hypertension health services to the patients in a safe, confidential, and timely manner. The device, supported patients in treatment counseling; delivering medications to the patients; accounting for the types of medications delivered, quantity, and amount of fees the patients pays at the time of delivery (like an Mpesa transaction); and also connecting the patients with their doctor whenever they needed.. In doing so, a peer collected health information from the patients on a regular basis on this mobile device.

A peer was someone living with hypertension/pressure in the community who had been successful in managing their hypertension. The peer was responsible for a number of things:

- Delivering hypertension medication to people living with hypertension/pressure at their most convenient location (door-to-door medication delivery).
- Confirming payment of medication (Mpesa transaction) by people living with hypertension/pressure before issuing the medication.
- Providing psychological support to people living with hypertension/pressure during medication delivery and whenever needed.
- Recording the health progress of people living with hypertension/pressure in a mobile device whenever they are in contact with a person living with hypertension/pressure.
- Using the mobile device, communicate with a clinician, to discuss the progress of an individual living with hypertension.
- Whenever it was necessary, they enabled a conversation (intervention: either audio or video) between the clinician and the patient using the mobile device at the patient's convenient location.

1. What did you think about this peer-led project in supporting individuals living with hypertension in the community?

Probe:

- What parts of the project did you like? Why?
- What part of the project didn't you like? Why?
- Parts of the project that were easily carried out? Why?
- Parts of the project that were difficult to carry out? Why?

2. What were the advantages of this kind of peer-led program?

Probe:

- Advantages of peers leading the delivery of health services
- Advantages of door to door drug delivery
- Advantages of peers providing psychological support to individuals living with hypertension at the community level
- Advantages of peers recording health information of the individuals receiving hypertension medication at the community on the mobile device (Probe: quality of care, provider-patient communication, privacy and confidentiality)

- Advantages of doctor and the patient having a clinical meeting using a mobile device at the community level (Probe: quality of care, provider-patient communication, privacy and confidentiality)

3. What were the disadvantages of this kind of peer-led program?

Probe:

- Disadvantages of peers leading the delivery of health services
- Disadvantages of door to door drug delivery
- Disadvantages of peers providing psychological support to individuals living with hypertension at the community level
- Disadvantages of peers recording health information of the individuals receiving hypertension medication at the community on the mobile device (Probe: quality of care, provider-patient communication, privacy and confidentiality)
- Disadvantages of doctor and the patient having a clinical meeting using a mobile device at the community level (Probe: quality of care, provider-patient communication, privacy and confidentiality)

4. In what ways did this peer-led program affect the management of hypertension at the community level?

Probe:

- How did it affect medication adherence for individuals living with hypertension?
- How did it affect follow-up of individuals living with hypertension?
- How did it effect on how hypertension is perceived in the community?

5. In what ways did this peer-led program affect the management of hypertension at the facility level?

Probe:

- Positive effects (How did this program complement the efforts in clinic?)
- Negative effects (How did this make it challenging to manage hypertension at the clinic level)

6. In what ways did this peer-led affect the way care for hypertension/pressure is offered during the current COVID pandemic?

B. Peers

*Now let us talk more specifically about the peers who delivered these health services to individuals living with hypertension at the community.*

7. *What are your perception about the peers that were used to implement the PT4A intervention*

Probe:

- *characteristics of the peer*
- *Qualifications/skill*
- *Training*
- *Integrity*

C. Mobile device

*Now let us talk more about the mobile device used to deliver these health services to individuals living with hypertension at the community.*

8. What is your perception of mobile device used by the peers to deliver the PT4A intervention?
9. What are the mobile device features that were most useful in implementing the PT4A intervention?

Probe:

- Type of device
- Size of device
- Connectivity
- Content
- Data flow
- Care facilitation features

10. What were the mobile device features that were not useful in implementing the PT4A intervention?

Probe:

- Type of device
- Size of device
- Connectivity
- Content
- Data flow
- Care facilitation features

11. What was your perception about the mobile payment mode used to pay for the Hypertension medications in the PT4A intervention?

12. How did the use of a mobile device impact the delivery of hypertension services at the community?

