staff and peers will receive study specific training on the need to at all times maintain participant confidentiality, in addition to receiving training in good clinical practice (GCP) and human subjects' protection (HSP) training. The HIT platform builds on the AMPATH OpenMRS system which encompasses patient data protection measures such as restricted access to authorized users only, which will further maintain patient confidentiality. We will recruit **up to 100** patients from among these three facilities, targeting an equal number per county. In case there is a report of an adverse reaction to medications or new symptom by the participant to the peer during the pilot phase of the study, all peer navigators will be guided by a decision support system built into the HIT that will require the prompt notification of one of the two local pharmacist investigators in the study, as well as the patient's clinician. The peer will contact directly both the pharmacist investigator(s) and the appropriate clinician. Swift action will be taken based on the advisement of the clinician. Inclusion criteria will include age greater than 18 years, and currently enrolled in the AMPATH CDM program. Exclusion criteria will include acute illness requiring immediate medical attention, terminal illness, or inability to provide informed consent.

We will collect data through a survey on process and implementation measures such as completeness of the peer delivery, satisfaction of the patients, patient activation, and fidelity of delivery strategy. We will conduct FGDs with patients and clinicians then conduct KII (Key informant interviews) with the peer delivery agents, focusing on contextual issues impacting implementation, suggestions for modifications, and concepts of feasibility (Table 3). The target group size for the FGDs is 6-10 participants but if there are insufficient numbers, we will accommodate a smaller size. FGD transcripts, data management, and analysis will be performed as described above. We have used this approach previously with success.

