- Providing psychological support to people living with hypertension/pressure during medication delivery and whenever needed.
- Recording the health progress of people living with hypertension/pressure in a mobile device whenever they are in contact with a person living with hypertension/pressure.
- Using the mobile device, communicate with a clinician, to discuss the progress of an individual living with hypertension.
- Whenever it was necessary, they enabled a conversation (intervention: either audio or video) between the clinician and the patient using the mobile device at the patient's convenient location.

*I would first like to ask you questions regarding your perception and experience with the PT4A project*

18. What did you think about this peer-led project in supporting you as an individual living with hypertension in the community?

Probe:

- What parts of the project did you like? Why?
- What part of the project didn't you like? Why?

19. What were your experiences with peers leading the delivery of hypertension services in the community?

Probe:

- What did you like? Why?
- What didn't you like? Why?

20. What were your experiences with peers delivering medication at your convenient location in the community?

Probe:

- What did you like? Why?
- What didn't you like? Why?

21. What were your experiences with peers providing psychological support to you in the community?

Probe:

- What did you like? Why?
- What didn't you like? Why?

22. What is your perception of peers recording your health information on a mobile device?

Probe:

- Privacy and confidentiality.

23. What is your perception of you and the doctor having a clinical meeting using a mobile device at the community?

Probe:

- Quality of care
- Provider-patient communication
- Privacy and confidentiality

24. What is your perception about the mobile payment mode used to pay for the Hypertension medications in the PT4A intervention?

25. What are your perceptions about the characteristics of the peers who delivered the hypertension services to you at the community?

Probe:

- Age
- Gender
- Personality
- Academic qualification
- Skill/Training

26. In what ways did this peer-led program affect your hypertension care?

Probe:

- How did it affect your medication adherence?
- How did it affect your clinic adherence?
- How did it affect the quality of care you received?

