**D. PT4A intervention:**

*There is a plan to start a project that will support people living with hypertension/pressure at the community level. The purpose of the project is to assist these individuals take hypertension/pressure medication as required through a peer-led project. This peer led project will use a mobile device similar to regular mobile phone, a smart phone, or a tablet. The mobile device will enable us to deliver hypertension health services to the patients in a safe, confidential, and timely manner. With the device, we will support the patients in treatment counseling; delivering medications to the patients; accounting for the types of medications delivered, quantity, and amount of fees the patients pays at the time of delivery (like an Mpesa transaction); and also connecting the patients with their doctor whenever they need.. To do so, a peer will need to collect health information from the patients on a regular basis on this mobile device.*

*A peer will be someone who is living with hypertension/pressure in the community and has been successful in managing their hypertension. The peer will be responsible for a number of things:*

- *Deliver hypertension medication to people living with hypertension/pressure at their most convenient location (door-to-door medication delivery).*
- *Confirm payment of medication (Mpesa transaction) by people living with hypertension/pressure before issuing the medication.*
- *Provide psychological support to people living with hypertension/pressure during medication delivery and whenever needed.*
- *Record the health progress of people living with hypertension/pressure in a mobile device whenever they are in contact with a person living with hypertension/pressure.*
- *Using the mobile device, communicate with a clinician, to discuss the progress of an individual living with hypertension.*
- *Whenever necessary enable a conversation (intervention: either audio or video) between the clinician and the patient using the mobile device at the patient's convenient location.*

*I would first like to ask you questions regarding your perception and experience with the PT4A project*

1. Could you kindly describe your role in the PT4A intervention?

2. What was your general perception of the PT4A intervention project?

Probe:

- What parts of the project did you like? Why?
- What part of the project didn't you like? Why?
- Parts of the project that were easily carried? What made it easy?

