**NB: To be completed for each participant**

**Focus Group Discussion Guide**  
**Design Team**

**Opening Remarks:** Human-centered design is a creative approach to problem solving. It emphasizes issues that are important to community stakeholders rather than leadership or administrators. This design process is focused on understanding the needs of the community, generating many ideas from different perspectives, building tangible prototypes, and iteratively improving the solution based on stakeholder feedback.

During our Design Team meetings, we worked through phases of Inspiration, Brainstorming, Conceptualization, Creation, and Iteration. Through this process, we have learned much about the human-centered design methods and how they may be used to create a combined health information technology (HIT) and peer support program for PT4A. We have asked you to participate today because you have been a part of the PT4A Design Team. The purpose of this discussion is to reflect on your experience during the design process and provide feedback to the facilitators.

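### The pilot's focus group and interview scripts vouch for the device's confidentiality before asking respondents about it

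*Combined protocol and SAP*

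**What the plan says.** The main protocol, Sub Aim 2.2, sets out the pilot's qualitative sessions: "We will conduct FGDs with patients and clinicians then conduct KII (Key informant interviews) with the peer delivery agents". Appendix C holds a guide for each of these three groups, plus one for the design team at its sixth meeting.

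In the clinical team guide and the guide for individuals living with hypertension, a descriptive block under part A (PT4A intervention) comes after the ground rules and before the first question. Both contain the sentence: "The mobile device enabled us to deliver hypertension health services to the patients in a safe, confidential, and timely manner". The peer guide has a parallel block, worded as a plan: "The mobile device will enable us to deliver hypertension health services to the patients in a safe, confidential, and timely manner".

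All three guides then return to confidentiality. The clinician and peer guides attach the prompt "Probe: quality of care, provider-patient communication, privacy and confidentiality" to items on recording health information and on remote consultations. The patient guide asks "What is your perception of peers recording your health information on a mobile device" (question 22) and follows with a privacy prompt, which is repeated in question 23.

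The guides also contain neutral wording. The opening remarks of each tell respondents "There is no wrong or right response", and the clinician guide asks "What were the disadvantages of this kind of peer-led program".

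**The concern.** Saying that peers used a tablet describes the intervention. Saying that the device made the service safe, confidential and timely evaluates it, and the evaluation is in the study team's own voice. A respondent who is then asked about privacy has to contradict the moderator in order to report a problem.

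These sessions are meant to find contextual problems, suggested modifications and views on feasibility. Under Design Team Meeting #6 in Appendix A, issues raised in focus groups are grouped into themes, turned into updates, and carried into the final model intended for wider use. A muted confidentiality problem might therefore not reach that model. The direction of any distortion favours PT4A.

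**Working it through.** No sample size, rate or test is involved, so the check is a comparison of texts: where the sentence stands, what it asserts, and which of those assertions the same guide later asks about.

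**Guide by guide (Appendix C)**

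| Guide | Sentence before first question? | Tense | Privacy and confidentiality probes |
|---|---|---|---|
| Clinical team focus group | Yes | Past | 4 (questions 2 and 3, two each) |
| Patient focus group | Yes | Past | 2 (questions 22 and 23) |
| Peer interview | Yes | Future | 2 (question 3, two items) |
| Design team, meeting 6 | No | – | 0 |

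The total is 4 + 2 + 2 = 8 probes, across 3 of the 3 pilot guides and 3 of the 4 guides in Appendix C.

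**How the eight are framed.** Two of the clinician probes sit under advantages and two under disadvantages. The two patient probes follow questions about perception. The two peer probes follow a question about experience. So 2 + 2 + 2 + 2 = 8, and only two of the eight ask outright for a negative.

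**Attribute by attribute.**
- Confidential: asserted in all three guides and probed in all three.
- Safe: asserted in all three, asked about directly in none.
- Timely: asserted in all three, asked about directly in none.
- Quality of care: probed in all three, but not asserted by the sentence.

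The overlap between what is asserted and what is asked is therefore one attribute.

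**Counterweight by respondent.** Clinicians are asked for disadvantages on privacy specifically. Peers are asked what they disliked about the project and the device, and what was difficult. Patients get like and dislike probes in questions 18 to 21, but not in questions 22 and 23, where privacy comes up. The group whose information is at stake thus has the thinnest counterweight at that point. Peers have a different difficulty. With one agent at each of three facilities there are 1 × 3 = 3 of them, they are paid from study funds, and they are trained to keep confidentiality, so reporting a breach could mean reporting their own lapse.

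**Is the sentence needed?** The sentences that follow it in each script already list what the device did: support counselling and delivery, account for medicines and fees, and connect patient and doctor. The acceptability survey scripts in Appendix B introduce the peer and device roles without it.

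**The case against.** The strongest reply is that one clause sits inside guides that otherwise invite criticism. Respondents are asked for honest opinions and told there are no right answers; the focus groups are also told that differing views are expected. The clinician guide asks about negative effects at the clinic, peer integrity and device features that were not useful; the peer guide also asks about unhelpful features. This stands as mitigation. It does not remove the lead: the general reassurance comes before the evaluative sentence, and the patient privacy questions carry no negative prompt.

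Several stronger readings are tempting, and the documents do not support them.

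- A reader might infer that respondents are told the answer on safety and timeliness too. None of the three guides asks about either directly.
- A reader might infer that all three scripts report a result. The peer script is a forward-looking promise. Its separate fault is that it introduces a completed pilot as something still planned.
- A reader might infer that breaches and late deliveries would go unseen. The Appendix B patient questionnaires ask whether peers can be trusted with private information, and whether medication came on the expected date and at the expected time. Their introductions lack the sentence. Suppression is a risk here, not something shown.
- A reader might infer that every session under Appendix C is affected. The design team guide lacks the sentence, and its declared aim is different: "The purpose of this discussion is to reflect on your experience during the design process and provide feedback to the facilitators". It does also ask how patients and providers received the intervention.
- A reader might infer that respondents generally depend on the study for employment. The documents show study pay for the peers; they do not show it for patients or facility clinicians.

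**Conclusion.** The point holds for confidentiality. In all three pilot guides the study team vouches for it before the first question and then asks about it, as a stated outcome for clinicians and patients and as a promise for peers. The lead favours PT4A, is partly offset, and is least offset in patient questions 22 and 23. Its size is unknown and cannot be derived from the documents.

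Two assumptions matter. The first is that moderators deliver the block as written. Appendix C gives no explicit instruction to read it aloud, but it is first-person moderator script. The second is that the sessions are those named in the main protocol's Sub Aim 2.2.

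This is a modest but worthwhile correction to the qualitative feasibility evidence. It gives no ground for doubting the pill count adherence ratio, the fidelity measure or the change in systolic blood pressure, none of which comes from these sessions.

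**What to change.** 1. Delete the evaluative sentence from the clinical team, patient and peer guides. No replacement is needed, because the following text already lists the device's functions.
2. Put the introductory block of the peer guide in the past tense, since the interview asks about completed work in the pilot.
3. Add the like and dislike probes of patient questions 18 to 21 to questions 22 and 23.

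The cost is a wording amendment to three guides, with any ethics review that the revised instruments require. The guides carry 2022 dates and the protocol version is dated November 2022, so the documents do not show whether sessions had already taken place. If they had, keep the data, state the wording used, and report it as a limitation of the confidentiality findings.
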